### 3.5 Duration of Follow Up

Duration of follow up:

- Those subjects who complete preoperative therapy and achieve either CR/PR/SD with R0 or R1 resection, and complete 9 cycles of continued pembrolizumab-based combination therapy (with pembrolizumab dosing as 400 mg Q6W) will be followed for up to 12 additional months, or until disease progression, death, unacceptable toxicity or withdrawal of consent, whichever occurs first.
- Those subjects who complete preoperative therapy and achieve either CR/PR/SD with R2 resection, or achieve a pre-operative CR but do not undergo CN, and complete 18 cycles of continued pembrolizumab-based combination therapy (with pembrolizumab dosing as 400 mg Q6W) will be followed for up to 12 additional months, or until disease progression, death, unacceptable toxicity or withdrawal of consent, whichever occurs first.
- Subjects who experience disease progression will have the mandatory safety follow-up visit 30 days (+7 days) after the last dose of study treatment. All AEs that occur prior to the Safety Follow-Up Visit should be recorded. Subjects with an AE of Grade >1 will be followed until the resolution of the AE to Grade 0-1 or until the beginning of a new anticancer therapy, whichever occurs first. Serious AEs that occur within 90 days of the end of treatment should also be followed and recorded.
- Subjects removed from study for any reason other than disease progression, death, or AEs will have a mandatory safety follow-up visit within 30 days for the final study treatment.

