### 5.1.2 Cohort B: Pembrolizumab + Axitinib

#### 5.1.2.1 Safety Lead-In

The first 6 subjects accrued to Cohort B will be evaluated to test the safety of the combination of pembrolizumab and axitinib. All 6 subjects in Cohort B will be followed for 28 days after surgery for excessive post-operative complications before additional subjects are enrolled to each combination cohort. If  $\leq 1$  subject experience Grade IV/V surgical complications per the Clavien-Dindo classification (Appendix 3), then 11 additional evaluable subjects will be accrued to the cohort. If  $\geq 2$  subjects experience Grade IV/V surgical complications, or if  $\geq 2$  subjects experience a delay in surgery beyond the specified 14-21 day window following the end of the preoperative treatment period (that is, 14-21 days from Cycle 3, Day 21; delays for scheduling, operating room scheduling or patient preference are not included), then the cohort will be halted to accrual, and the safety data reviewed to modify the protocol as appropriate, including changes in dose level

(Section 5.1). If the cohort is re-opened with a change in dose level, an additional 6 subjects will be accrued to evaluate safety. If  $\leq 1$  subject experience a Grade IV/V surgical complication, then 11 additional subjects will be accrued to the cohort at the reduced dose. If  $\geq 2$  subjects experience a Grade IV/V surgical complication, the cohort will be terminated for lack of safety. Therefore, a minimum of 4, and a maximum of 36 subjects may be accrued into Cohort B.

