#### **6.1.2.5 Cytoreductive Nephrectomy and/or Metastasectomy**

Complete the following tests within 14 days of CN and/or MET:

- CBC with differential and platelet count
- Blood chemistry assessment, including:
- ALP, ALT/AST, total bilirubin, calcium, phosphorus, BUN, creatinine, total protein, albumin, fasting glucose, potassium, sodium, chloride, bicarbonate, uric acid, LDH
- Thyroid Function Tests: TSH, FT4, T3
- Coagulation assessment (PT, PTT, INR)
- Immune parameter assessments
- Urinalysis, (including microscopic exam, if abnormal results are noted)

Subjects will undergo CN and/or MET no sooner than 2 weeks following the final cycle of preoperative pembrolizumab-based therapy. The final cycle of preoperative therapy concludes after the conclusion of the last day (21st day) of the 3rd cycle of pembrolizumab-based therapy. A window of 7 days will be allowed for surgical planning and scheduling (thus, CN and/or MET will occur 14 days [+7 days] following the final cycle of preoperative therapy). Complete the following procedures on the day of surgery:

- CN and/or MET (performed per standard of care).
- Tissue collection for study purposes (see Laboratory Manual for details).
- Pathology assessment (as clinically indicated, per standard of care).

The subject may be consented for core tumor biopsies if CN and/or MET cannot be performed following preoperative pembrolizumab-based therapy for any reason, including:

- Unequivocal disease progression
- AEs
- Development of a concurrent, unrelated medical illness that deems subject inoperable
- Subject withdrawal of consent
- Investigator or surgeon deems inoperable for any reason
- Subjects may be consented for multiple tumors to be biopsied if safe and feasible.
- Subjects who achieve a radiographic CR and have locally advanced disease will proceed with CN.

Subjects who become ineligible for CN and/or MET while on study, and do not consent to provide a tumor biopsy (if safe and feasible), will be removed from study. See section 8.2.2 for details regarding replacement policy.

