#### 6.1.2.6 Postoperative Therapy, Day 1 of Each Cycle

Following CN/MET, continuation of pembrolizumab-based therapy for patients who achieved pre-operative CR/PR/SD will proceed as follows:

- Subjects with an R0 resection (NED, margins negative) or R1 resection (microscopic disease, margins positive) will continue receiving their assigned pembrolizumab-based combination therapy for up to 9 cycles or until disease progression, death, unacceptable toxicity, or withdrawal of consent, whichever occurs first
- Subjects with an R2 resection (macroscopic disease after surgery), or who had a pre-operative CR but did not undergo CN, will continue receiving their assigned pembrolizumab-based combination therapy for up to 18 cycles or until disease progression, death, unacceptable toxicity, or withdrawal of consent, whichever occurs first.
- Subjects may resume therapy following CN/MET as soon as 21 days following surgery (subjects with metastatic disease who have a CR during the preoperative period and therefore do not undergo MET will have no interruption in their therapy). Prior to resuming therapy, the subject must be evaluated by their surgeon and appropriate wound healing must be documented. Subjects with wound healing complications that have not resolved with 42 days of CN and/or MET will discontinue study participation. Any subject who

cannot resume study therapy within 42 days of CN/MET will discontinue study participation.

Perform the following study procedures on Day 1 of each cycle ( $\pm 3$  days) unless stated otherwise:

- Directed physical examination
- Vital signs and weight
- ECOG performance status
- Evaluation of AEs
- Concomitant medications
- CBC with differential and platelet count
- Blood chemistry assessment, including:
  - ALP, ALT/AST, total bilirubin, calcium, phosphorus, BUN, creatinine, total protein, albumin, fasting glucose, potassium, sodium, chloride, bicarbonate, uric acid, LDH
- Thyroid Function Tests: TSH, FT4, T3
- Blood for correlative studies (including immune monitoring) at week 15 only
- Urinalysis (including microscopic exam, if abnormal results are noted)
- Treatment:
  - All cohorts, metastatic disease and achieved CR:
    - Pembrolizumab 400 mg IV (Day 1) Q6W
  - Cohort A (all other subjects continuing therapy):
    - Pembrolizumab 400 mg IV (Day 1) Q6W
  - Cohort B (all other subjects continuing therapy):
    - Pembrolizumab 400 mg IV (Day 1) Q6W
    - Axitinib (Days 1 - 42). Dose titration per standard of care

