#### 6.1.3.2 Safety Follow-Up

The mandatory Safety Follow-up Visit should be conducted 30 days (+7 days) after the last dose of study treatment or before initiation of a new anticancer treatment, whichever comes first. All AEs that occur prior to the Safety Follow-up Visit should be recorded. Subjects with an AE of Grade >1 will be followed until the resolution of the AE to Grade 0-1 or until the beginning of a new anticancer therapy, whichever occurs first. Serious AEs (SAEs) that occur within 90 days of the end of treatment or before initiation of a new anticancer treatment should also be followed and recorded.

The following procedures will be performed at the Safety Follow-up Visit:

- Directed physical examination
- Vital signs and weight
- ECOG performance Status
- Evaluation of AEs
- Concomitant medications
- Urinalysis (including microscopic exam if abnormal results are noted)
- CBC with differential and platelet count
- Blood chemistry assessment, including:
  - ALP, ALT/AST, total bilirubin, calcium, phosphorus, BUN, creatinine, total protein, albumin, fasting glucose, potassium, sodium, chloride, bicarbonate, uric acid, LDH
- Thyroid function tests: TSH, FT4, T3

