- Includes alkaline phosphatase (ALP), aspartate aminotransferase/alanine aminotransferase (ALT/AST), total bilirubin, calcium, phosphorus, blood urea nitrogen (BUN), creatinine, total protein, albumin, fasting glucose, potassium, sodium, chloride, bicarbonate, uric acid, lactate dehydrogenase (LDH)
- Laboratory evaluations may be omitted if they were already performed within 7 days of Cycle 1, Day 1
- Window for these specific assessments is within the 14 days prior to CN and/or MET
- Women of childbearing potential require a negative urine test within 72 hours prior to the first dose of study treatment. Serum test is only required if urine test is positive or is not evaluable. Additional urine pregnancy testing can be conducted if required by local regulations or clinically indicated.

- f. Administered for up to 1 year (9 cycles) (for patients who undergo CN/MET with R0 or R1 resection), or up to 2 years (18 cycles) (for patients who undergo CN/MET with R2 resection or who had a pre-operative CR but did not undergo CN), or until death, disease progression, unacceptable toxicity, or withdrawal of consent.
- g. To be done every 2 cycles (i.e., about every 3 months) during postoperative pembrolizumab-based treatment
- h. If prior scan was done within 6 weeks, does not have to be repeated (per physician discretion)
- i. Those subjects who undergo CN/MET with R0 or R1 resection who complete 1 year (9 cycles) of postoperative pembrolizumab-based therapy, or those patients who undergo CN/MET with R2 resection or who had a pre-operative CR but did not undergo CN and complete 2 years (18 cycles) of postoperative pembrolizumab-based therapy, will have scans Q12W for up to 12 additional months, or until disease progression, death, unacceptable toxicity or withdrawal of consent, whichever occurs first.
- j. Imaging evaluation (CT chest, abdomen and pelvis; MRI if CT is contraindicated; IV contrast given unless contraindicated; Bone scan if clinically indicated; MRI brain if clinically indicated), for tumor assessment
- k. In subjects who complete postoperative pembrolizumab-based therapy: end of treatment visit will be performed within 7 days of the last dose of study drug or discontinuation
- l. In subjects who complete postoperative pembrolizumab-based therapy: additional safety follow-up visit is not necessary; the follow-up visit will be done during the 12 month follow-up period
- m. At the time of disease progression (subjects will require additional consent)

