### 6.3.2 Withdrawal from the Study

A subject must be withdrawn from the study if the subject or subject's legally acceptable representative withdraws consent from the study.

A subject must be withdrawn from the study if there is evidence of unequivocal disease progression without evidence of clinical benefit during the preoperative treatment period. Subjects with PD during the preoperative treatment period who, in the opinion of the treating physician and principal investigator, are likely to benefit from CN/MET AND in whom surgery is safe and feasible, may proceed with CN/MET on study. Subjects in whom CN/MET is unlikely to provide benefit OR surgery is not safe and feasible, may still be consented to core tumor biopsy on study, if safe and feasible and, in the judgment of the treating physician, the biopsy will not delay appropriate standard of care. Subjects will withdraw from study participation following CN/MET or tumor biopsy. If CN/MET and tumor biopsy are not safe and feasible and not in the best interests of the subject, the subject will withdraw from study participation immediately.

If a subject withdraws from the study, they will no longer receive study treatment or be followed at scheduled protocol visits.

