## **7.8 Reporting Events to Merck**

All AEs, SAEs and other reportable safety events that occur after the ICF is signed but before treatment allocation must be reported by the investigator if the subject is receiving placebo run-in or other run-in treatment, if the event causes the subject to be excluded from the study, or is the result of a protocol-specified intervention, including but not limited to washout or discontinuation of usual therapy, diet, or a procedure.

- All AEs from the time of treatment allocation through 30 days following cessation of study treatment must be reported by the investigator.
- All AEs meeting serious criteria, from the time of treatment allocation/randomization through 90 days following cessation of study treatment, or 30 days following cessation of study treatment if the subject initiates new anticancer therapy, whichever is earlier, must be reported by the investigator.
- All pregnancies and exposure during breastfeeding, from the time of treatment allocation/randomization through 120 days following cessation of study treatment, or 30 days following cessation of study treatment if the subject initiates new anticancer therapy, must be reported by the investigator.
- Additionally, any SAE brought to the attention of an investigator at any time outside of the time period specified above must be reported immediately to the Merck clinical team if the event is considered to be drug related.

Investigators are not obligated to actively seek AE or SAE or other reportable safety events in former study subjects. However, if the investigator learns of any SAE, including a death, at any time after a subject has been discharged from the study, and he/she considers the event to be reasonably related to the study treatment or study participation, the investigator must promptly notify the Merck clinical team.

All initial and follow-up AEs, SAEs and other reportable safety events will be recorded and reported to the Merck clinical team or designee within the timeframes as indicated in Table 10.

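### The documents conflict on the anchor for the safety visit and AE window; on the last-dose reading, routine AE collection in Cohort A ends before surgery for operated subjects who do not restart

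*Combined protocol and SAP*

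**What the plan says.** Surgical complications by Clavien-Dindo grade are part of the secondary safety endpoint (2.2.2, 8.1). No collection window is attached to them there.

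The safety visit and AE windows are anchored in different ways:

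- Section 3.5, for subjects who progress: "Subjects who experience disease progression will have the mandatory safety follow-up visit 30 days (+7 days) after the last dose of study treatment".
- Section 6.1.3.2, for subjects in general: "The mandatory Safety Follow-up Visit should be conducted 30 days (+7 days) after the last dose of study treatment", or before a new anticancer treatment if that comes first.
- Section 7.8: "All AEs from the time of treatment allocation through 30 days following cessation of study treatment must be reported by the investigator". SAEs run to 90 days after cessation, or to 30 days if new anticancer therapy starts.
- Section 6.1.3.1 and Table 7 footnote w: timing is relative to the last dose or to discontinuation.

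Surgery is scheduled from the end of Cycle 3: "CN and/or MET will occur 14 days [+7 days] following the final cycle of preoperative therapy". The AE review in the CN/MET column of Table 7 carries footnote d: "Window for these specific assessments is within the 14 days prior to CN and/or MET".

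On subjects with progression who are operated on study, 6.3.2 says: "Subjects will withdraw from study participation following CN/MET or tumor biopsy". It adds that withdrawn subjects are no longer seen at scheduled visits. For slow recovery, 6.1.2.6 says: "Subjects with wound healing complications that have not resolved with 42 days of CN and/or MET will discontinue study participation".

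The one explicit postoperative period is in the Cohort B lead-in (5.1.2.1): "All 6 subjects in Cohort B will be followed for 28 days after surgery for excessive post-operative complications".

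**The concern.** A drug-anchored window suits drug toxicity. Surgical complications need a window that starts at the operation. Here the operation comes 34-41 days after the last preoperative pembrolizumab dose, so a 30-day window from that dose can close before surgery takes place.

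For subjects who restart therapy this does little harm, because they have an AE review at the Week 15 dosing visit. Operated subjects who do not restart never reach that visit. The Table 7 review attached to surgery is placed before it, and the day-of-surgery list in 6.1.2.5 contains no AE evaluation.

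At stake is the completeness of the Clavien-Dindo tabulation. Section 3.1 makes safety around surgery the objective of Cohort A and singles out surgical complications. A missed event can only lower the count.

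**Working it through.** **Calendar, with Cycle 1 Day 1 as day 1 and 21-day cycles (Study Schema, Table 3)**

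- Cycle 3 Day 1 = 1 + 2 × 21 = day 43, the last preoperative pembrolizumab dose.
- Cycle 3 Day 21 = 43 + 20 = day 63, the last preoperative axitinib day in Cohort B, assuming it is taken to the end of the cycle.
- Surgery = 63 + 14 to 63 + 21 = day 77-84 (5.1.2.2, 6.1.2.5).

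This reproduces Table 7. Week 7 begins on day 6 × 7 + 1 = 43. Week 12 begins on day 11 × 7 + 1 = 78, inside the surgical window. Week 15 begins on day 14 × 7 + 1 = 99, which is 21 days after day 78 and matches the earliest permitted restart.

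**Last-dose reading, operated subject who does not restart**

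Each closing day is compared with surgery on day 84 and on day 77.

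| Window from last dose | Cohort A (day 43) | Relative to surgery | Cohort B (day 63) | Relative to surgery |
|---|---|---|---|---|
| All AEs, 30 days | day 73 | 4-11 days before | day 93 | 9-16 days after |
| Safety visit, 30-37 days | day 73-80 | 11 days before to 3 days after | day 93-100 | 9-23 days after |
| SAEs, 90 days | day 133 | 49-56 days after | day 153 | 69-76 days after |
| SAEs under 7.8 with new therapy, 30 days | day 73 | 4-11 days before | day 93 | 9-16 days after |

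**Discontinuation reading**

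If discontinuation is dated to the day of surgery, the safety visit falls 30-37 days after it. If it is dated to 42 days after surgery, the visit falls at 42 + 30 to 42 + 37 = 72-79 days. For the same Cohort A subject, the safety visit can therefore precede surgery or follow it by a month or more, depending on which section is applied.

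**Subjects with progression**

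Section 3.5 gives them a safety visit. Section 6.3.2 withdraws them after surgery and ends scheduled visits. Both cannot be followed for an operated subject whose visit is still due. Section 3.1 puts the risk of preoperative progression at 10%: about 0.10 × 12 = 1.2 subjects in Cohort A and 0.10 × 84 = 8.4 in the whole study. Only those actually operated on count.

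**Size, by assumption only**

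The documents give no complication rate and no non-restart rate. Let f be the share of operated subjects who do not restart, m the share of their complications missed, and r their complication rate relative to the others. Then

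observed/true = [(1 − f) + f·r·(1 − m)] / [(1 − f) + f·r].

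- f = 0.10, m = 0.5, r = 1: 0.95/1.00 = 0.95.
- f = 0.10, m = 0.5, r = 2: 1.00/1.10 = 0.91.
- Over f = 0.05-0.15, m = 0.25-1 and r = 1-2, the ratio runs from 0.99 to 0.74.

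**Lead-in halt rule (2 or more of 6)**

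At an assumed true Grade IV/V rate of 20%, the probability of a halt is 1 − 0.8⁶ − 6 × 0.2 × 0.8⁵ = 0.345. If 10% of events were missed (rate 0.18), it would be 0.296. That loss is not expected here, because Grade IV/V events are life-threatening or fatal (Appendix 3). They therefore meet the seriousness criteria in 7.3.3.2 and fall under the 90-day window.

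**The case against.** The strongest reply is that the anchor is ambiguous rather than wrong. Footnote w and 6.1.3.1 allow discontinuation as the starting point. Table 7 also lists CN/MET under study treatment, so cessation of study treatment in 7.8 could include surgery. On those readings the safety visit falls at least 30 days after surgery, and 6.1.3.2 requires AEs before that visit to be recorded. This stands as a limit: the early closure is one reading of the text. It does not remove the problem, because 3.5 and 6.1.3.2 state the last dose without that alternative.

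A reader might infer that every operated subject who does not restart escapes observation. The documents do not support that. Sections 6.1.2 and 6.3.1 keep subjects who stop for toxicity under follow-up, and 7.5 follows AEs to resolution. A subject who leaves with an unresolved wound complication leaves because it was seen. The exposed group is mainly subjects operated on after progression.

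A reader might also infer that the halt rule is undermined. It is little affected. The 90-day SAE window covers most Grade IV/V events, the Cohort B lead-in has its own 28 days, and Appendix 2 has the DSMC review all participant data in the lead-in. The exception is a Cohort A subject who does not restart and begins new anticancer therapy. Even then, 7.8 requires late SAEs to be reported if considered drug related.

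Finally, 7.8 governs reporting to the drug supplier, and Appendix 2 enters all Grade 3-5 AEs with no stated cut-off. Both points are fair. They narrow the likely loss to lower-grade, non-serious complications, but neither supplies a collection window for the Clavien-Dindo endpoint.

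**Conclusion.** The point holds as an inconsistency that should be fixed. Stated rules conflict on the anchor and on follow-up of operated subjects with progression, and one reading ends routine AE collection in Cohort A before the operation. What can be lost is mainly lower-grade, non-serious complications in operated subjects with progression, plus SAEs in Cohort A when new anticancer therapy starts.

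Under-counting is the likely direction. Its size cannot be derived, and the ratios of 0.95 and 0.91 rest on assumed capture and complication rates. The stronger conclusion, that surgical safety is shown to be biased low, goes beyond the documents: it takes the last-dose reading as settled and needs rates that they do not give. Surgical safety is reported descriptively, so no formal test depends on it. The timeline assumes no dose delays and surgery within its stated window.

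**What to change.** 1. Reconcile the anchors in 3.5, 6.1.3.1, 6.1.3.2, 7.8 and Table 7 footnote w, so that each operated subject has one date from which the safety visit and AE windows run.
2. Attach a collection window to the Clavien-Dindo endpoint: all grades, for every operated subject, through at least 28 days after CN/MET, whether or not the subject progresses, restarts or begins new therapy. The 28 days is the period 5.1.2.1 already uses. Routine postoperative records can supply the data.
3. State that, for data collection, the 6.3.2 withdrawal of operated subjects with progression takes effect only after that assessment, and align this with 3.5.
4. Add a postoperative AE review to Table 7 beside the preoperative one under footnote d.

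The cost is protocol wording, one CRF page, and about four more weeks of data collection for subjects with progression. No treatment or surgical rule changes.
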